5.4 Duration of Follow Up

Patients who discontinue treatment for reasons other than disease progression will be followed with CT scans at 6 and 12 months or until disease progression or next therapy for PFS and DOR endpoints. Follow-up after treatment discontinuation for progression, or after documented progression following discontinuation of therapy for reasons other than progression initially, will be by phone every 6 months for up to 1 year after the discontinuation of treatment for OS endpoints. Patients removed from study for unacceptable adverse event(s) will be followed until resolution or stabilization of the adverse event.

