5.5 Criteria for Removal from Study

Patients will discontinue study treatment when any of the criteria listed in Section 5.3 applies. Patients will be removed from study after the follow-up period outlined in Section 5.4, or if they decide to withdraw from the study. The reason for study removal and the date the patient was removed must be documented in the Case Report Form.

In the event of unusual or life-threatening complications, participating investigators must immediately notify the Principal Investigator [name] at [contact] or [contact] (page through operator).

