d: Cycle 2 and on, electrocardiograms (EKGs) will be done on day 1 of each cycle. EKGs should be done per standard of care at the treating institution. EKGs are not required to be in triplicate, but if there is an issue with a QTc value on the single EKG, an average QTc is acceptable on three triplicate EKGs if it makes a patient eligible for treatment.
e: Adverse event and concomitant medication evaluation will be assessed at each visit by the clinical trial personnel.
f: If bone marrow biopsy is negative at screening, it does not need to be repeated. If the bone marrow biopsy is involved at baseline, it must be repeated in order to confirm a complete response (CR).
g: To be collected in 1 x 4 mL purple top EDTA tube. However, a minimum of 1 mL of blood is needed so any tube size that meets this 1 mL minimum is acceptable. This can be shipped along with the frozen tissue.
h: Serum pregnancy test (women of childbearing potential).
i: Off-treatment evaluation. Patients who come off treatment for progression will have telephone follow-up every 6 months for up to 1 year

- | |
|--|
| 
for OS endpoints. Patients who come off treatment for reasons other than progression will have CT scans (see below) at 6 and 12 months, or until the time of progression or next therapy, for PFS and DOR endpoints.
 
j: CT scans will be repeated at 6 and 12 months, or until the time of progression, for patients who come off study for reasons other than disease progression.
 
k: Biopsy or sample of most accessible tissue, which may be bone marrow, body fluid, lymph node, or other tumor site. The sample should be from the same tumor source (ie body fluid, bone marrow, lymph node, or other tumor site) at each timepoint. This is distinct from the bone marrow biopsy required at screening for lymphoma staging. However, if the bone marrow is involved at screening, this can be used as the site of tumor biopsy for patients during pre-treatment, cycle 1 and at the time of progression. Biopsies during cycle 1 should optimally be done on day 17, but can be done between days 17-22.
 |
|--|

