13.4 Analysis of Secondary Endpoints

Secondary endpoints will be analyzed at the same time as the primary endpoint and assessed for each cohort separately and overall. Due to the small sample size in each cohort and all patients combined, secondary endpoints will be descriptive unless otherwise noted. All eligible patients who receive at least one dose of treatment will be included in efficacy endpoints, and all patients regardless of eligibility who receive at least one dose of treatment will be included in toxicity assessments.

Patients receiving any treatment regardless of eligibility or study completion will be assessed for toxicity from the time of their first treatment. At each toxicity evaluation, patients with unacceptable toxicities will be removed from study but remain in safety evaluations. Toxicities will be summarized with counts and proportions within each cohort and overall.

Time-to-event endpoints of progression-free and overall survival (PFS and OS, resp.) will be characterized using the Kaplan-Meier method. OS is defined from the date of study entry until the date of death by any cause. PFS will be measured from the date of study entry until documentation of first progression or death from any cause. Median follow-up time will be assessed using the reverse Kaplan-Meier method.

Duration of response (DOR) is defined as the time from first objective response (PR or CR) until the first date of documented progression using [the response criteria] or death due to any cause. For patient who remain alive without progression, the DOR will be censored on the date of their last response assessment. Patients who begin a subsequent therapy without prior documented progression will be censored at the last response assessment prior to initiation of non-protocol therapy. DOR will be evaluated only in patients who respond with either a PR or CR while on study.

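### OS contact ends 1 year after treatment stops and is unspecified after next therapy without progression, so OS censoring is informative and the curve is probably too high beyond 12 months

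*Combined protocol and SAP*

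**What the plan says.** - **Who gets OS contact (Section 5.4).** The trigger is "Follow-up after treatment discontinuation for progression, or after documented progression following discontinuation of therapy for reasons other than progression initially". Contact is then "by phone every 6 months for up to 1 year after the discontinuation of treatment for OS endpoints".
- **Patients who stop for another reason (Section 5.4).** They "will be followed with CT scans at 6 and 12 months or until disease progression or next therapy for PFS and DOR endpoints". OS is not named for this group.
- **Study calendar, footnote i.** "Patients who come off treatment for progression will have telephone follow-up every 6 months for up to 1 year". Those who stop for other reasons have CT at 6 and 12 months, "or until the time of progression or next therapy, for PFS and DOR endpoints".
- **End of participation (Section 5.5).** "Patients will be removed from study after the follow-up period outlined in Section 5.4".
- **Analysis (Section 13.4).** OS runs from study entry to death from any cause, by Kaplan-Meier. DOR has censoring rules; OS has none. Secondary endpoints are descriptive. For toxicity stops, "patients with unacceptable toxicities will be removed from study but remain in safety evaluations". On timing, "Secondary endpoints will be analyzed at the same time as the primary endpoint".

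**The concern.** Kaplan-Meier is valid when patients censored at a given time have the same outlook as those still followed. Here the last planned contact is set by how long the patient stayed on treatment, and treatment lasts as long as the patient benefits and tolerates it. Early failures leave the risk set first. The later part of the curve is then carried by long-treated patients, and their lower death rate is applied to everyone.

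A second gap affects patients who stop without progression. CT follow-up ends at next therapy, and phone contact waits for documented progression, so a patient who moves to another therapy first has no survival contact specified. This is not confined to toxicity: Section 5.3 takes all patients off treatment by 31 May 2020, so some may stop while still benefiting.

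At stake is the descriptive OS curve for each cohort of 10 to 20 patients. OS is a named secondary objective, and the protocol anticipates that a randomised trial could follow.

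**Working it through.** **1. No plan figure to reproduce.** The documents give no OS median, rate, event count or power. All survival inputs below are assumptions.

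**2. Horizon.** Last planned OS contact = time on treatment + 12 months. The first response scan is at 8 weeks, so an early progressor reaches 2 + 12 = month 14. A patient treated for 10 months reaches 10 + 12 = month 22. No one reaches the cap before month 12.

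**3. Two-group calculation.** Assume 75% non-responders with exponential survival (median *m*, 6 to 12 months), capped at month 14, and 25% responders with median 24 months, capped at month 22. Between months 14 and 22 only responders are at risk, so

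KM(t) = S(14) × R(t)/R(14), where R(t) = 2^(−t/24), N(t) = 2^(−t/m) and S(t) = 0.75 N(t) + 0.25 R(t).

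With m = 12: S(14) = 0.75 × 0.4454 + 0.25 × 0.6674 = 0.5009. KM(18) = 0.5009 × 0.8909 = 0.446. True S(18) = 0.75 × 0.3536 + 0.25 × 0.5946 = 0.414.

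| m (months) | KM / true at 18 | Bias | KM / true just before 22 | Bias |
|---|---|---|---|---|
| 6 | 28.1% / 24.2% | +3.9 | 25.1% / 19.1% | +5.9 |
| 8 | 34.7% / 30.6% | +4.1 | 30.9% / 24.4% | +6.5 |
| 12 | 44.6% / 41.4% | +3.3 | 39.8% / 34.3% | +5.5 |

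At risk after month 14 in a cohort of 20: 20 × 0.25 × 0.6674 = 3.3 patients.

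**4. Wider simulation of the cap alone** (400,000 patients per scenario). Assumptions: response rate 5 to 40%; median time to progression 10 months (responders) and 2 months (non-responders); median survival after progression 6 to 18 and 4 to 8 months respectively; 15% of patients assigned a possible non-progression stop at 0.5 to 4 months. Across scenarios the bias was 0.0 at 6 and 12 months, +0.4 to +0.9 at 15, +1.1 to +2.9 at 18, and +2.7 to +7.5 at 24. Example (25% responders; post-progression medians 18 and 8 months): true OS 56.8%, 40.2% and 29.0% at 12, 18 and 24 months; estimated 56.8%, 43.0% and 36.5%.

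**5. Adding the next-therapy gap.** Response rate 20%, post-progression medians 18 and 8 months, 20% assigned a possible non-progression stop, and half of those who stop this way lost one month later at next therapy. Bias in points:

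| Survival of those who stop without progression | 6 mo | 12 mo | 24 mo | 24 mo, cap alone | Gap's share at 24 mo |
|---|---|---|---|---|---|
| Worse (median 3 months after stopping) | +1.4 | +1.9 | +8.4 | +7.2 | 8.4 − 7.2 = +1.2 |
| No different | −0.2 | −0.4 | +7.1 | +7.3 | 7.1 − 7.3 = −0.2 |
| Better (median 30 months) | −0.4 | −1.2 | +5.1 | +6.0 | 5.1 − 6.0 = −0.9 |

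Varying the share lost and their survival more widely gave about −2 to +3 points at 12 months.

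**6. Section 5.4 against footnote i.** Take a patient who stops for toxicity and progresses four months later. Section 5.4 moves the patient to phone contact. Footnote i ends CT at progression and gives phone contact only to those whose treatment ended for progression. A site working from the calendar would lose this patient for OS at progression.

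**The case against.** **The consequence is small.** OS is descriptive, with no test or target, and the decision rules use response only. With 20 patients and the inputs of step 3, the sampling standard deviation of the Kaplan-Meier estimate is about 11 to 14 points at 18 months and 11 to 15 at 22, well above the bias. This stands and limits the weight of the point. It does not remove it: sampling error is visible in a confidence interval, while this bias is not and has a likely direction.

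**The whole curve is not biased upward.** A reader might infer that it is. The cap censors no one before month 12, and the next-therapy gap has no fixed sign. Section 5.4 also does not say that progression must precede next therapy to trigger phone contact, so some of these patients might still enter it. But their CT schedule has ended, so nothing planned would document the progression.

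**Section 13.4 does not drop toxicity stops from efficacy.** A reader might infer this from the removal sentence. It says only that they stay in safety evaluations. The same section keeps all eligible treated patients in the efficacy endpoints, Section 5.4 uses similar removal wording for patients still being followed, and Section 5.5 separates stopping treatment from leaving the study. The wording is loose; it is not a further censoring rule.

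**Loss of follow-up through analysis timing is not shown.** Secondary endpoints are analysed with the primary, but no date is given for the primary analysis.

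**Conclusion.** The point holds within limits. The written follow-up rule makes OS censoring depend on time on treatment, so it is informative. The upward direction beyond 12 months rests on the death rate being higher after stopping than during treatment, which is likely but assumed. The size, about +1 to +4 points at 18 months and +3 to +7.5 at 22 to 24 months, rests on survival inputs that the documents do not supply. Up to 12 months, and for a median OS below 12 months, the cap has no effect. The missing follow-up after next therapy is a separate defect that can act earlier and in either direction. The conflict between Section 5.4 and footnote i is a matter of text and needs no assumption. The ORR analysis and the cohort decisions are untouched.

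**What to change.** - **Section 5.4 and footnote i:** collect survival status by phone or record check for every treated patient, from study entry to death or one common cut-off, whatever the reason for stopping and regardless of progression or next therapy. Use the same rule in both places.
- **Section 13.4:** add an OS censoring rule (date last known alive) and analyse OS at that cut-off.
- **Sections 5.4, 5.5 and 13.4:** reconcile the removal wording so that stopping for toxicity does not end PFS and OS follow-up.
- **If follow-up cannot be extended:** do not report Kaplan-Meier OS beyond 12 months from entry, and still obtain vital status to 12 months for patients who start next therapy without progression. Truncation cures the cap but not that gap.

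The cost is a few calls or record checks for each of at most 50 patients, plus protocol wording. Enrolment closed in October 2019 (February 2019 for ALCL and MCL), so some patients already off study may need re-contact. The consent pages were not available for this review, so whether existing consent covers that is unknown.

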5.5 Criteria for Removal from Study

Patients will discontinue study treatment when any of the criteria listed in Section 5.3 applies. Patients will be removed from study after the follow-up period outlined in Section 5.4, or if they decide to withdraw from the study. The reason for study removal and the date the patient was removed must be documented in the Case Report Form.

In the event of unusual or life-threatening complications, participating investigators must immediately notify the Principal Investigator [name] at [contact] or [contact] (page through operator).

6. DOSING DELAYS/DOSE MODIFICATIONS

There will be up to two dose reductions allowed (120mg/m² and 80mg/m²) for intolerable grade 2 toxicity or the equivalent of dose limiting toxicities. Dose delays up to 14 days will be allowed for any persistent grade 2 adverse events (AE) (with the exception of fatigue, weakness, skin toxicity, and/or laboratory abnormalities) with treatment resumption when the AE resolves to grade 1 or better; AST or ALT > 3x the upper limit of normal, with treatment resumption when the AE resolves to grade 1 or better; and any AE, laboratory abnormality or condition that, in the judgment of the investigator, warrants delaying the dose of study medication.

The dose is determined by the patient's weight on Cycle 1 Day 1, regardless of changes in body weight. The dose can be rounded base on the intuitional guidelines of the treating institution.

Dose Level	AT13387 (onalespib) Dose
-2	80 mg/m ² /dose d1,2,8,9,15,16
-1	120 mg/m ² /dose d1,2,8,9,15,16
0	160 mg/m ² /dose d1,2,8,9,15,16

Below are dose modification tables for the following adverse events: nausea, vomiting, diarrhea, neutropenia, and thrombocytopenia.

Nausea	Management/Next Dose for AT13387 (onalespib)
≤ Grade 1	No change in dose
Grade 2	Hold until ≤ Grade 1. Resume at same dose level.
Grade 3	Hold* until < Grade 1. Resume at one dose level lower, if indicated.**
Grade 4	Off protocol therapy

*Patients requiring a delay of >2 weeks should go off protocol therapy.

**Patients requiring > two dose reductions should go off protocol therapy.

Recommended management: antiemetics.

Vomiting	Management/Next Dose for AT13387 (onalespib)
≤ Grade 1	No change in dose
Grade 2	Hold until ≤ Grade 1. Resume at same dose level.
Grade 3	Hold* until < Grade 1. Resume at one dose level lower, if indicated.**
Grade 4	Off protocol therapy

*Patients requiring a delay of >2 weeks should go off protocol therapy.

**Patients requiring > two dose reductions should go off protocol therapy.

Recommended management: antiemetics.

Diarrhea	Management/Next Dose for AT13387 (onalespib)
≤ Grade 1	No change in dose
Grade 2	Hold until ≤ Grade 1. Resume at same dose level.
Grade 3	Hold* until < Grade 1. Resume at one dose level lower, if indicated.**
Grade 4	Off protocol therapy

*Patients requiring a delay of >2 weeks should go off protocol therapy.

**Patients requiring > two dose reductions should go off protocol therapy.

Recommended management: Loperamide antidiarrheal therapy

Dosage schedule: 4 mg at first onset, followed by 2 mg with each loose motion until diarrhea-free for 12 hours (maximum dosage: 16 mg/24 hours)

Adjunct anti-diarrheal therapy is permitted and should be recorded when used.

Neutropenia	Management/Next Dose for AT13387 (onalespib)
≤ Grade 2	No change in dose
Grade 3,4	Hold* until < Grade 2. Resume at one dose level lower, if indicated.**

*Patients requiring a delay of >2 weeks should go off protocol therapy.

**Patients requiring > two dose reductions should go off protocol therapy.

Recommended management: G-CSF support.

Thrombocytopenia	Management/Next Dose for AT13387 (onalespib)
≤ Grade 1	No change in dose
Grade 2	Hold until ≤ Grade 1. Resume at same dose level.
Grade 3,4	Hold* until < Grade 1. Resume at one dose level lower, if indicated.**

*Patients requiring a delay of >2 weeks should go off protocol therapy.

**Patients requiring > two dose reductions should go off protocol therapy.

Recommended management: platelet transfusion support per institutional guidelines.

Visual impairment including peripheral flashes (photopsia), blurred or double vision, floaters, color distortion and dimness, difficulties with light/dark accommodation, tunnel vision or other field defects, halos, apparent movement of stationary objects, and complex disturbances. Symptoms are generally Grade 1, intermittent, reversible, and transient, lasting a few seconds to a few minutes and occurring on 1- 3 days/cycle. Doses may need to be held in the setting of grade 1-2 toxicity, and treatment may need to be discontinued if toxicity is ≥ grade 3.

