5.1.1 AT13387 (onalespib)

The study drug AT13387 (onalespib) will be administered by intravenous infusion via peripheral or central venous access at a dose of 160mg/m² (using actual body weight from cycle 1 day 1 to calculate body surface area) over 1 hour. The dosing frequency will be on days 1, 2, 8, 9, 15, and 16 of every 4 week cycle. AT13387 (onalespib) will be provided by CTEP.

On the first day of treatment each week (days 1, 8, and 15), patients must meet the following pre-treatment criteria: ANC \geq 1000/mcL, platelet count $>$ 75,000/mcL (or $>$ 30,000/mcL if due to disease), potassium and magnesium above the institutional lower limit of normal (repletion is allowed).

Astex has recommended that vital signs (temperature, heart rate, blood pressure, oxygen saturations) be performed pre-AT13387 (onalespib) infusion. Additional vital signs will be performed during the course of infusion as clinically indicated. No extended post-administration monitoring will be required, except as indicated in the protocol for research-related assays.

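### The dose-modification text, the five toxicity tables and the platelet criteria do not agree on when to reduce, when to hold and when to resume

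*Combined protocol and SAP*

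**What the plan says.** The opening text of Section 6 allows up to two dose reductions "for intolerable grade 2 toxicity or the equivalent of dose limiting toxicities". It allows delays of up to 14 days for persistent Grade 2 adverse events, "with treatment resumption when the AE resolves to grade 1 or better", but excepts fatigue, weakness, skin toxicity and laboratory abnormalities. It applies the same resumption grade to raised AST or ALT. A last clause lets the investigator delay for any other event or abnormality by judgment, with no resumption grade.

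Five tables follow:

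- **Nausea, vomiting, diarrhea.** Up to Grade 1 the instruction is "No change in dose". At Grade 2 it is "Hold until ≤ Grade 1. Resume at same dose level". At Grade 3 it is "Hold* until < Grade 1. Resume at one dose level lower, if indicated". At Grade 4 the patient goes off therapy.
- **Thrombocytopenia.** The same thresholds apply, with Grades 3 and 4 sharing the stricter row.
- **Neutropenia.** Up to Grade 2 there is no change. At Grades 3 and 4 the instruction is "Hold* until < Grade 2. Resume at one dose level lower, if indicated".

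The Grade 3 (or 3,4) holds carry a footnote: "Patients requiring a delay of >2 weeks should go off protocol therapy".

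Section 5.1.1 adds that on days 1, 8 and 15 "patients must meet the following pre-treatment criteria". These cover ANC, platelets, potassium and magnesium. Platelets must exceed 75,000/mcL, or 30,000/mcL if the low count is due to disease. Section 3.1.7 makes a matching eligibility allowance, at 30,000/mcL or above, for marrow involvement.

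**The concern.** A multi-center trial needs one answer when a treating team asks whether to reduce, hold, resume or stop. Here the answer can depend on whether the team reads the text, the table row for the current grade, the table row for the original event, or the pre-dose criteria. Two of the mismatches set the text against the tables. A third lies within each table and becomes consequential through the 2-week footnote. The fourth concerns patients whom the eligibility criteria deliberately admit. What is at stake is consistent safety handling across sites, and how treatment discontinuations are understood afterwards.

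**Working it through.** The plan states no figure on this point, so the check sets the rules side by side.

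**1. Grade 2 reductions.** The text permits a reduction for Grade 2 toxicity judged intolerable. Four tables have a Grade 2 hold row (nausea, vomiting, diarrhea, thrombocytopenia), and all four resume at the same level. In the neutropenia table Grade 2 falls in the no-change row. No table provides for a Grade 2 reduction.

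**2. Grade 2 laboratory abnormalities.** The text takes laboratory abnormalities out of the Grade 2 delay rule and leaves them to the investigator's judgment. The thrombocytopenia table holds at Grade 2 without reference to judgment. A low platelet count is a laboratory abnormality, so the two rules give different instructions.

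**3. Release grade against no-change grade.**

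| Table | Highest grade with no change | Highest grade that releases a Grade 3 (or 3,4) hold | Difference |
|---|---|---|---|
| Nausea | 1 | 0 | 1 − 0 = 1 |
| Vomiting | 1 | 0 | 1 − 0 = 1 |
| Diarrhea | 1 | 0 | 1 − 0 = 1 |
| Thrombocytopenia | 1 | 0 | 1 − 0 = 1 |
| Neutropenia | 2 | 1 | 2 − 1 = 1 |

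In all five tables there is exactly one grade at which a recovering patient fits the no-change row but is not released by the hold row. In the first four tables that is Grade 1, and in the neutropenia table it is Grade 2. A patient who stays there for more than 2 weeks goes off therapy under the footnote. Under the no-change row the same patient would be dosed.

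**4. Disease-related platelets.** Section 7.2 specifies CTCAE 5.0 for adverse-event reporting, but the protocol does not print the platelet cut-offs. Assume Grade 2 is 50,000 to <75,000/mcL and Grade 3 is 25,000 to <50,000/mcL. Let B be the boundary between Grades 1 and 2. Section 5.1.1 accepts disease-related counts above 30,000, while the table holds below B. The overlap therefore runs from just above 30,000 to just below B.

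- B = 75,000 (assumed): overlap 30,001 to 74,999. A count of 60,000 meets the Grade 2 hold row, and 31,000 meets the Grade 3,4 hold row.
- B = 50,000 (for range): overlap 30,001 to 49,999.
- B at or below 30,000: no overlap.

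Under the assumed cut-offs, every count that only the disease allowance admits falls in a hold row of the table.

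**The case against.** The best defense of item 3 is that rows are chosen by the grade of the event. The no-change row would then serve an event that never went higher, and the stricter release would serve recovery from a worse one. That is coherent, and the strict inequality recurs in all five tables, which may point to intent. It stands to this extent: item 3 is an unexplained mismatch, not a strict logical contradiction. The documents do not state the intent, though.

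On item 1, the text is permissive and limited to intolerable toxicity, so the Grade 2 rows could be read as a default. On item 2, the judgment clause permits a hold for a laboratory abnormality. Neither reading is written down. On item 4, the criteria in Section 5.1.1 are necessary conditions, not sufficient ones, and the table may be meant for drug toxicity only. But if the table applies on top, the disease allowance has no effect under the assumed cut-offs, and the table does not limit itself to drug-related counts.

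Several stronger readings are tempting, and the documents do not support them:

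- **That the text's resumption rule contradicts the Grade 3 rows.** The rule is stated for Grade 2 events and for AST/ALT. It agrees with the gastrointestinal Grade 2 rows and sets no resumption grade for Grade 3.
- **That Section 5.1.1 conflicts with the nausea, vomiting and diarrhea rows.** It does not mention those events.
- **That removal before the 8-week scan counts as treatment failure and so lowers the response rate and power.** The study calendar schedules PET/CT and CT off treatment. Section 11.1.2.2 runs best response until progression, not until the last dose. Section 13.5.2 fails response categories 4 to 9, not early discontinuation as such.
- **That the adverse-event rates in Section 2.2.1.2 size the problem.** Diarrhea at 78%, nausea at 53% and vomiting at 32% are overall frequencies, and 49.1% is any Grade 3/4 event of any kind. None counts patients who recover from Grade 3 to exactly Grade 1 and stay there beyond 14 days.

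**Conclusion.** The point holds as a set of wording inconsistencies in safety rules. Items 1 and 2 are differences between the Section 6 text and its own tables and need no outside source. Item 3 is a one-grade gap in each of five tables, which may be deliberate but is not said to be; the footnote turns it into removal from therapy. Item 4 rests on assumed platelet cut-offs and holds for any boundary between Grades 1 and 2 above 30,000/mcL.

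The number of patients affected cannot be derived. The nearest figure in the documents is serious diarrhea in 5 of 104 patients, all resolved, and that does not measure the contested situations. No effect on response rate or power is established. The practical reach is also limited: enrollment closed in October 2019 and all study treatment had to end by May 31, 2020, so only patients still on treatment could be handled differently.

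**What to change.** The sponsor should reconcile Sections 3.1.7, 5.1.1 and 6 so that:

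- each of the five toxicities has one recovery rule, marked as intended where it differs from the no-change row;
- one statement says how Grade 2 reductions in the text relate to the Grade 2 rows;
- one statement says whether and how Grade 2 laboratory abnormalities lead to a hold;
- one statement says how disease-related thrombocytopenia is handled under the table.

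Which rule applies in each case is the sponsor's decision. The cost is protocol wording and notice to sites. Design, sample size and analysis are untouched. The gain is uniform safety handling for patients still on treatment.

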3.1.6 Life expectancy of greater than 3 months

3.1.7 Patients must have normal organ and marrow function, and electrolyte balance (allowing for repletion) as defined below:

- absolute neutrophil count $\geq 1,000/\text{mcL}$
- platelets $\geq 75,000/\text{mcL}$, unless due to marrow involvement by lymphoma in which case a platelet count of $\geq 30,000/\text{mcL}$ will be used
- total bilirubin $\leq 1.5x$ ULN, unless due to Gilbert's syndrome or hemolysis, in which case $\leq 3.0x$ ULN is allowed.
- AST(SGOT)/ALT(SGPT) $\leq 3.0 \times$ institutional upper limit of normal
- creatinine $\leq 1.5x$ ULN or a creatinine clearance $\geq 50 \text{ mL/min}/1.73 \text{ m}^2$ for patients with creatinine levels above institutional normal.
- Potassium above the institutional lower limit of normal (supplementation to meet this is allowed)
- Magnesium above the institutional lower limit of normal (supplementation to meet this is allowed)

3.1.8 HIV+ patients are eligible for the trial provided they meet the other study criteria in addition to the following:

- CD4+ T-cells $\geq 250/\text{mm}^3$
- HIV sensitive to antiretroviral therapy
- Zidovudine not allowed
- Long term survival anticipated on the basis of HIV alone were it not for the lymphoma
- No concurrent AIDS-defining illness other than the lymphoma

- 3.1.9 The effects of AT13387 (onalespib) on the developing human fetus are unknown. For this reason, women of child-bearing potential and men must agree to use adequate contraception (hormonal or barrier method of birth control; abstinence) prior to study entry, for the duration of study participation, and for 4 months after the completion of AT13387 (onalespib) administration. Should a woman become pregnant or suspect she is pregnant while she or her partner is participating in this study, she should inform her treating physician immediately. Men treated or enrolled on this protocol must also agree to use adequate contraception prior to the study, for the duration of study participation, and 4 months after completion of AT13387 (onalespib) administration.

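### Entry and weekly pre-dose rules allow for disease-related low platelets, but the Section 6 thrombocytopenia table does not, so one patient can get opposite dosing instructions

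*Combined protocol and SAP*

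**What the plan says.** **Entry (3.1.7).** The standard minimum is 75,000/mcL, "unless due to marrow involvement by lymphoma in which case a platelet count of" at least 30,000/mcL applies.

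**Weekly pre-dose check (5.1.1).** "On the first day of treatment each week (days 1, 8, and 15), patients must meet the following pre-treatment criteria". The platelet criterion is above 75,000/mcL, or above "30,000/mcL if due to disease".

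**Thrombocytopenia table (Section 6).** The row for Grade 2 instructs sites as follows: "Hold until ≤ Grade 1. Resume at same dose level". For the two highest grades, which share a single row, the instruction is different: "Hold* until < Grade 1. Resume at one dose level lower, if indicated". Neither row mentions cause or baseline count. The asterisk on the Grade 3,4 row leads to the footnote "Patients requiring a delay of >2 weeks should go off protocol therapy". The Grade 2 row carries no asterisk.

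**Section 6 text.** Delays of up to 14 days are allowed for persistent Grade 2 adverse events, "with the exception of fatigue, weakness, skin toxicity, and/or laboratory abnormalities". The same sentence also allows a delay for any laboratory abnormality that the investigator thinks warrants one. The tables are introduced as covering adverse events.

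**The concern.** The disease-related allowance is written out twice, at entry and at each treatment week, and is absent from the table that decides holding, resuming and stopping. Two sites could treat the same patient in opposite ways and both cite the protocol.

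Two things are at stake. The first is consistent conduct: under one reading a patient is dosed at a count the table says to hold, and under the other a patient is held at a count that Section 5.1.1 accepts. The second is the primary endpoint. Response is first assessed at about 8 weeks. A patient who starts treatment, is then held under the table and does not recover may stop before that scan. Section 13.5.2 keeps eligible patients in the main response analysis and treats categories 4-9, including not assessable, as failures. A removal caused by marrow disease could then be read as lack of drug activity.

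**Working it through.** **1. The rules side by side.** Section 7.2 names CTCAE version 5.0, but the documents print no platelet cut-points. Assumption for this table: Grade 1 from the lower limit of normal down to 75,000; Grade 2 below 75,000 to 50,000; Grade 3 below 50,000 to 25,000; Grade 4 below 25,000/mcL.

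| Disease-related count (/mcL) | Entry (3.1.7) | Pre-dose (5.1.1) | Assumed grade | Section 6 table |
|---|---|---|---|---|
| Above 30,000, below 50,000 | Admitted | Dose permitted | 3 | Hold until below Grade 1; off therapy if more than 2 weeks |
| 50,000 to below 75,000 | Admitted | Dose permitted | 2 | Hold until Grade 1 or lower; no removal rule on this row |
| 75,000 | Admitted | Dose permitted | 1 | No change |

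Under this assumption the whole band opened by the allowance is a hold under the table. After Grade 3,4 the target is no graded thrombocytopenia, which is stricter than the 75,000/mcL asked of patients without marrow disease.

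**2. Sensitivity to the cut-points.** The dosing conflict needs only that some counts between 30,000 and 75,000/mcL grade 2 or higher. The removal consequence needs some of them to be Grade 3 or higher. If the whole band were Grade 2, the hold conflict would remain but the 2-week footnote would not apply.

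**3. The plan's own operating characteristics (13.1, MCL and DLBCL).** Ten patients, stop at 0 responses, then ten more, success at 3 or more of 20. With X and Y the responses in each stage,

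P(success) = 1 − [P(X=0) + P(X=1)·P(Y≤1) + P(X=2)·P(Y=0)].

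- At 25%: 1 − [0.0563 + 0.1877 × 0.2440 + 0.2816 × 0.0563] = 1 − 0.1180 = 0.882.
- At 5%: 1 − [0.5987 + 0.3151 × 0.9139 + 0.0746 × 0.5987] = 0.069.

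Both match the stated 88% and 6.9%.

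**4. Illustration only.** Suppose a share f of would-be responders is dosed, removed under the table and counted as non-responders. The observable rate is 0.25 × (1 − f).

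| f (assumed) | Observable rate | P(success) |
|---|---|---|
| 0 | 25% | 88.2% |
| 5% | 23.75% | 85.8% |
| 10% | 22.5% | 82.9% |
| 20% | 20% | 75.9% |

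No value of f can be taken from the documents. The calculation does not describe the ALK+ ALCL cohort, which plans 10 patients with no two-stage rule.

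**The case against.** The best reply is one of scope. Section 6 speaks of toxicity and introduces its tables as covering adverse events, while Section 5.1.1 is the specific weekly rule and names disease-related counts. A site could sensibly apply 5.1.1 to baseline marrow-related counts and the table to treatment-emergent falls. That may be what was meant, but no text says so, and it does not settle a count that is low from disease and then falls further on treatment.

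Four other replies limit what follows:

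- A reader might infer that every patient admitted under the allowance would be held and then removed. The documents do not support this. The 2-week footnote is marked on the Grade 3,4 row only, removal depends on non-recovery, and the table itself recommends transfusion support.
- A reader might infer that the Section 6 laboratory wording flatly contradicts the Grade 2 hold. That sentence is permissive and goes on to allow delay for laboratory abnormalities at the investigator's judgment, so the two can be read together. It needs clarifying, no more.
- If the table governed from Cycle 1 Day 1, the patient would not be dosed at all. Section 4.4 lets such a registration be cancelled, 13.4 limits efficacy endpoints to patients with at least one dose, and 13.5.2 may leave out those who received none. The loss of power arises only if 5.1.1 governs the first dose and the table governs later ones.
- Stopping early does not mean going unassessed: the study calendar schedules PET/CT and CT at the off-treatment evaluation. Counting removed patients as non-responders is a possibility, not a certainty.

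Enrolment closed in October 2019 and treatment was to end by May 31, 2020, so rewording cannot restore power. It still matters for patients on treatment and for classifying past holds, removals and deviations.

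**Conclusion.** This is an internal inconsistency, held with moderate confidence. Sections 3.1.7 and 5.1.1 make an allowance for disease-related low platelets that the Section 6 table omits, and nothing states which prevails. The conflict over holding rests on one assumption: that counts of 30,000-75,000/mcL grade above 1. The consequence for therapy is narrower: a Grade 3,4 patient whose count does not recover to below Grade 1 within 2 weeks could be taken off because of the lymphoma rather than the drug. The consequence for response is narrower again: if already dosed, that patient could be counted as a non-responder under 13.5.2.

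The effect on response rate or power cannot be sized from the documents. The fall from 88% to 83-76% shows what an assumed 10-20% loss of would-be responders would do; a reader should not take it as an estimate of what this trial lost.

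**What to change.** Reconcile 3.1.7, 5.1.1 and the Section 6 thrombocytopenia table so that one rule states how disease-related low counts are handled for holding, resuming and going off therapy. The rule should say:

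- whether the table covers baseline or disease-related counts or only treatment-emergent falls;
- which section governs when 5.1.1 permits a dose and the table requires a hold;
- whether a prolonged Grade 2 hold leads to removal.

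Also state how the Section 6 laboratory-abnormality wording for Grade 2 relates to the table's Grade 2 platelet hold. The same Grade 3 wording appears in the nausea, vomiting and diarrhea tables, so the amendment should name the thrombocytopenia table.

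Which rule to adopt is the sponsor's clinical decision. The cost is protocol wording only. At analysis, list any patient who entered under the platelet allowance and any hold or removal for platelets, with the attributed cause, so that the number affected is known.
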